10.13.2. Schema

Figure 2: Schematic Overview of the Sub-Study

10.13.3. Schedule of Activities (SoA)

ApaRP Relugolix Sub-Study **participants join main ApaRP SoA after sub-study (starting Day 29 [C2D1 apa])*)*									
Study Visit	Pre-op Screening	Sub-Study V1				Sub-Study V2								Sub-Study V3	
Calendar Day		Day -14**	Day -13 to Day -8	Day -7	Day -6 to Day -1	Day 1	Day 2 to Day 6	Day 7	Day 8 to Day 13	Day 14	Day 15 to Day 20	Day 21	Day 22 to Day 27	Day 28	1
Study Window						+3 ^a								+3	Day
Screening/Administrative															le 2
Sub-study informed consent form (ICF) ^b	x*														t Cycl
Demographics	x*														g a
Review medical history requirements	x*														Ę
I/E criteria met	x*														star
Post-op PSA	x*														lo
Study Intervention Administration															to o
Dispense/administer study intervention (apalutamide)						x	x	x	x	x	x	x	x	x	RP pro
Dispense/administer study intervention (relugolix)		xc	x	x	x	x	x	x	x	x	x	x	x	x	I Apał
Check-in on medication compliance ^d				х		х		х		x		х		х	nair
Sub-study participant medication diary ^e		x	х	x	x	x	x	x	x	x	x	x	x	x	U 0
Efficacy Evaluations															Ĩ
Testosterone		х				xf								xf	ij
Safety Evaluations															ans
Focused physical examination including skin assessment ^g		x*													Ę
12-lead ECG	х					x								x	
Pharmacodynamics and Biomarkers															
Plasma samples ^h		x*													
Tumor tissue sample ⁱ		x*													
Pharmacogenomics (DNA)															
DRD status (germline)		x*													
Ongoing Participant Review															
Concomitant therapy							coi	ntinuo	us						
Adverse events ^k							co	ntinuo	us						
Education and counselling on skin care	continuous		1												

Key: ADT=androgen deprivation therapy; AE=adverse event; DNA=Deoxyribonucleic Acid; DRD=DNA repair deficient; ECG=electrocardiogram; ICF=informed consent form; I/E criteria=inclusion exclusion criteria; PSA=prostate-specific antigen

Footnotes:

*as required for main ApaRP study

**study Day -14 starts on date of administration of relugolix treatment

a If delaying sub-study visit 2 by up to 3 days, please advise the patient to continue relugolix until castrate levels of testosterone are confirmed and coadministration with apalutamide has started.

- Clinical Protocol 56021927PCR2041 Amendment 2
- b The sub-study ICF must be signed before first study-related activity and will cover the sub-study and the main study.
- c Relugolix administered as 360 mg on first day of treatment (Day –14), followed by 120 mg on subsequent days.
- d If not occurring during an in-person visit, the study team should call the participant to ask about medication compliance.
- e Should be completed daily by the participant during sub-study treatment and provided to the study team at each sub-study visit (form located in Section 10.14, Appendix 14).
- f If participant's testosterone ≥50 ng/dL on Day 1 or Day 28, stop relugolix, switch to intramuscular ADT, and switch to main ApaRP study.
- g Focused examinations are generally limited to the body system or regions based on participant's self-assessment and AE reporting. Any new complaints, symptoms reported by participants or adverse events noted by providers should guide the need and extent of physical examination.
- h Collected at baseline, 12 months or end of treatment, and at 24 months or progression (whichever comes first) as part of the main ApaRP study.
- i Tissue sample to be collected and sent to sponsor's laboratory partner along with a copy of the full histopathology report of the specimen. See Section 8.6 for further details.
- j Collection of concomitant therapies does not begin until time of first dose of relugolix.
- k Collection of AEs does not begin until time of first dose of relugolix.

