1.3. Schedule of Activities (SoA)

Study Visit	Pre-op Screening	Baseline V1	V2ª	V3ª	V4ª	V5ª	V6ª	V7ª/ET	V8ª Safety visit	F/U V9 ^b	F/U V10 ^b	F/U V11 ^b	F/U V12 ^b
Cycle/Cycle Day		C1/D1	C2/D1	C3/D1	C4/D1	C7/D1	C10/D1	C13/D1	C14/D1	C18/D1	C24/D1	C30/D1	C36/D1
Study Month		Month 1	Month 2	Month 3	Month 4	Month 7	Month 10	Month 13	Month 14	Month 18	Month 24	Month 30	Month 36
Screening/Administrative													
ICF ^c	Х												
Demographics	Х												
Review medical history requirements	х												
Phone call		Weekly check	Mid-cycle check	Mid-cycle check									
Inclusion and exclusion criteria met	х												
Post-op Screening PSA	Х												
Study Intervention Administration													
Dispense/administer study intervention		х	х	х	Xď	Xď	Xď						
Study intervention accountability			x	X	x	x	x	x					
ADT administration (with 3-month formulation) ^e		х			х	х	x						
Efficacy Evaluations													
PSA ^f					Х	X	X	X	X	X	X	X	X
Testosterone		Х			Х	Х	Х	Х	Х	Х	Х	Х	Х

Study Visit	Pre-op Screening	Baseline V1	V2ª	V3ª	V4ª	V5ª	V6ª	V7ª/ET	V8ª Safety visit	F/U V9 ^b	F/U V10 ^b	F/U V11 ^b	F/U V12 ^b
Cycle/Cycle Day		C1/D1	C2/D1	C3/D1	C4/D1	C7/D1	C10/D1	C13/D1	C14/D1	C18/D1	C24/D1	C30/D1	C36/D1
Study Month		Month 1	Month 2	Month 3	Month 4	Month 7	Month 10	Month 13	Month 14	Month 18	Month 24	Month 30	Month 36
Safety Evaluations													
Focused physical examinations ^g including skin assessment		х	х	x	x	x	х	х	х				
12-lead ECG ^h	Х												
Pharmacodynamics and Biomarkers													
Plasma samples ⁱ		Х						Х			X		
Tumor tissue sample		Х											
Pharmacogenomics (DNA)													
DRD status (germline)		Х											
Ongoing Participant Review													
Concomitant therapy ^k		Х	Х	Х	Х	X	Х	Х	Х	Х	X	X	Х
Adverse events ¹		Х	Х	Х	X	X	Х	Х	Х	X	X	X	X
Education and counselling on skin care		х	х	х	х	х	Х	х					

Note: Race, history of smoking and alcohol intake, height and weight at baseline will be recorded directly in the eCRF and will be considered as source data. Key: ADT=androgen deprivation therapy; AE=adverse event; C=cycle; CT=computed tomography; D=day; DNA=deoxyribose nucleic acid; DRD=DNA repair deficient; ECG=electrocardiogram; EOS=end of study; ET=end of treatment; F/U=follow-up; ICF=informed consent form; MRI=magnetic resonance imaging; pre-op=preoperative; PET=positron emission tomography; PSA=prostate-specific antigen; SOC=standard of care; USPI=United States Package Insert; V=visit.

Footnotes:

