- a Beginning with Visits 2 through 8, a window of ±7 calendar days for scheduling will be allowed.
- b Beginning with Visit 9 and for all follow-up visits, a window of ±14 calendar days for scheduling will be allowed.
- c Must be signed before first study-related activity.
- d Provide 3-month supply of apalutamide during Visits 4, 5, and 6.
- e ADT first administration will be at baseline and subsequently administered per USPI for total duration 12 months, 3-month depot is the preferred administration. NOTE: If 3-month DEPOT is used, the last dose will be administered at Month 10. If 3-month DEPOT is not used, follow USPI.

- Clinical Protocol 56021927PCR2041 Amendment 2
- f A PSA level >0.2 ng/mL will be an indicator of BCR and will be confirmed within 3 to 4 weeks regardless of study visit and timing. Depending on timing, this may be captured as an unscheduled visit.
- g Focused examinations are generally limited to the body systems or regions based on participant's self-assessment and AE reporting. Any new complaints, symptoms reported by participants or adverse events noted by providers should guide the need and extent of physical examination.
- h ECG assessment at screening if not available from preoperative information.
- i Collected at baseline, 12 months or end of treatment, and at 24 months or progression (whichever comes first).
- j Tissue sample to be collected and sent to sponsor's laboratory partner along with a copy of the full histopathology report of the specimen. Biopsy tissue is preferred. See Section 8.6 for further details.
- k Collection of concomitant therapies does not begin until time of first dose of apalutamide.
- ^L Collection of AEs does not begin until time of first dose of apalutamide.

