10.13.4. Introduction

10.13.4.1. Study Rationale

Relugolix (ORGOVYXTM) is an orally available gonadotropin-releasing hormone (GnRH) receptor antagonist approved by the FDA on December 18, 2020 for the treatment of adult patients with advanced prostate cancer. Relugolix is administered at a loading dose of 360 mg on the first day of treatment, followed by 120 mg taken orally once daily. Relugolix is metabolized primarily by CYP3A and is a substrate for intestinal P-glycoprotein (P-gp). Clinical studies with rifampin, a combined P-gp and strong CYP3A inducer, decreased the AUC and C_{max} of relugolix by 55% and 23%, respectively. Consequently, the relugolix label suggests avoiding coadministration with combined P-gp and strong CYP3A inducers and if unavoidable, to increase the dose of relugolix to 240 mg once daily.¹⁹

Apalutamide is a strong inducer of CYP3A4 and a weak inducer of P-gp. Concomitant use of apalutamide with medications that are primarily metabolized by CYP3A4 and/or a substrate of P-gp can result in lower exposure of these medications. Apalutamide has been shown to reach steady state concentrations at 4 weeks.⁷

Given relugolix is the first and only approved oral GnRH antagonist and apalutamide is indicated in combination with a GnRH analog, there is a need to understand the clinical implications of combining relugolix and apalutamide in the clinic. Achieving and maintaining a castrate level of serum testosterone (<50 ng/dL) while on ADT is considered the gold standard assessment of achieving castration with GnRH analogs. Data from 899 participants (from Phase 1, 2, and 3 studies) with both relugolix and testosterone concentration data were combined for PopPK and PopPK/PD analyses.¹⁸ In simulated testosterone concentrations, relugolix dosed as low as 40 mg once daily following a loading dose of 360 mg achieved a median testosterone <50 ng/dL within 10 days.¹⁸ Relugolix dosed at 120 mg once daily following a loading dose of 360 mg achieved a testosterone <50 ng/dL in 90% of the simulations within 10 days.¹⁸ In the registrational Phase 3 HERO study of relugolix dosed at 120 mg once daily after a loading dose of 360 mg, the cumulative probability of testosterone suppression to <50 ng/dL on Day 4 and Day 15 were 56% and 98.7%, respectively.²⁴

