10.13.6. SUB-Study Design

10.13.6.1. Overall Design

This is a single-arm, open-label, multi-center sub-study of apalutamide and relugolix in 12 participants with high risk localized prostate cancer who are treatment naïve, documented to have no evidence of metastatic disease prior to study entry, who are between Day 29 and Day 90 post-RP, whose PSA is ≤ 0.2 ng/mL at study entry, and who have recovered from surgery, per the

clinical judgment of the investigator. Upon completion of the sub-study, participants will be transitioned into the main ApaRP study protocol beginning at Cycle 2 Day 1.

The sub-study will be conducted in approximately 6 urology practices already conducting the main ApaRP study. There will be one study intervention group receiving relugolix monotherapy for 2 weeks followed by coadministration with apalutamide for 1 cycle (28 days). Treatment with relugolix will start following screening and completion of RP and no later than postoperative Day 90. Coadministration of apalutamide will start 14 days after initiation of relugolix monotherapy. Serum testosterone will be measured on Day -14 (ie, day of starting relugolix administration), Day 1 (ie, the day of starting coadministration with apalutamide), and Day 28. If a participant does not achieve a serum testosterone <50 ng/dL on Day 1 following 14 days of relugolix monotherapy, relugolix will be discontinued and the participant will switch to intramuscular ADT and the main ApaRP study and that participant will be replaced in the sub-study. If a participant achieves a serum testosterone <50 ng/dL on Day 1 following 14 days of relugolix monotherapy, coadministration with apalutamide will begin. As assessed on Day 28, if the coadministration of apalutamide and relugolix achieves and maintains a serum testosterone <50 ng/dL through Day 28 of the sub-study, participants will be given the opportunity to continue relugolix and apalutamide as part of the main ApaRP study. If the coadministration of apalutamide and relugolix does not achieve and maintain a testosterone <50 ng/dL through Day 28 of the sub-study in 2 or more participants, all participants on the sub-study will discontinue relugolix and switch to intramuscular ADT plus apalutamide as part of the main ApaRP study.

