The sub-study will have 12 participants. If 2 or more participants have a testosterone $\geq 50 \text{ ng/dL}$ on Day 28, the sub-study will be considered negative and all participants will switch to intramuscular ADT in the main ApaRP protocol. If 0 or 1 participant has a testosterone $\geq 50 \text{ ng/dL}$, the sub-study will continue until all 12 participants have been enrolled.

If a participant ends the sub-study early (ie, due to treatment non-compliance or not achieving a testosterone <50 ng/dL on Day 1 after relugolix monotherapy), that participant will be replaced in order to enroll 12 participants total. If the sub-study is terminated early due to lack of efficacy (ie, ≥ 2 participants have a testosterone $\geq 50 \text{ ng/dL}$ on Day 28) or safety (ie, ≥ 2 participants have prolonged QTc (\geq ULN) on Day 28), no further participants will be enrolled into the sub-study.

The timing and frequencies of study assessments are presented in the sub-study SoA (Section 10.13.3, Appendix 13). Efficacy assessments include serum testosterone and will be assessed at baseline (Day -14), after 14 days of relugolix monotherapy (Day 1), and after 28 days of coadministration of apalutamide and relugolix. A serum testosterone <50 ng/dL is considered castrate and the gold standard for indicating castration while on ADT. Study enrollment is defined as the day when the participant receives the first dose of relugolix monotherapy after having met all prescreening criteria. Adverse events will be assessed continuously from the time of enrollment and during treatment. A 12-lead electrocardiogram (ECG) will be conducted at screening, after 14 days of relugolix monotherapy, and after 28 days of apalutamide and relugolix coadministration, to examine QT prolongation. If any participant has a prolonged QTc at either Day 1 or Day 28, that participant will be removed from the study completely and replaced in the sub-study. If

2 participants have prolonged QTc at Day 28 the sub-study will terminated and any participants currently on the combination of relugolix and apalutamide will be evaluated for potentially changing to intramuscular ADT.

A diagram of the study design is provided in Section 10.13.2, Appendix 13, Schema.

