Relugolix, an FDA approved and commercially available oral ADT, not provided by the sponsor, will be administered per the ORGOVYX USPI during the sub-study and the main ApaRP study if participants continue relugolix coadministration (see Section 10.13.6.1, Appendix 13, Overall Design for details of relugolix continuation in the main ApaRP study). For further information on relugolix refer to the ORGOVYX USPI. For a definition of apalutamide overdose, refer to Section 6.7, Treatment of Overdose, in the main ApaRP protocol.

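### For men who stay on relugolix after the sub-study, the mandatory switch at testosterone of 50 ng/dL or more stops at Day 28, and the next scheduled draw is Day 85

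*Protocol*

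**What the plan says.** **Rules in the sub-study.** Protocol 10.13.3, footnote f, sets the individual rule: "testosterone ≥50 ng/dL on Day 1 or Day 28, stop relugolix, switch to intramuscular ADT, and switch to main ApaRP study". Section 10.13.6.1 adds a group rule. If two or more men reach 50 ng/dL on Day 28, "the sub-study will be considered negative and all participants will switch to intramuscular ADT in the main ApaRP protocol". Section 10.13.11 uses the same Day 28 count to call the sub-study negative.

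**Continuation.** If castration holds through Day 28, "participants will be given the opportunity to continue relugolix and apalutamide as part of the main ApaRP study" (10.13.6.1). They join the main schedule at Cycle 2 Day 1. Section 10.13.8.1 says that relugolix "will be administered per the ORGOVYX USPI during the sub-study and the main ApaRP study if participants continue relugolix coadministration".

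**Main-study schedule.** Protocol 1.3 has no testosterone draw at C2/D1 or C3/D1. After baseline, the draws up to the end of treatment are at C4/D1, C7/D1, C10/D1 and C13/D1. Footnote a reads: "Beginning with Visits 2 through 8, a window of ±7 calendar days for scheduling will be allowed".

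**Thresholds in the main study.** The only testosterone threshold is 150 ng/dL, which defines recovery (Protocol 9.4.3, SAP 5.4). SAP 5.1 times events from the first apalutamide dose, and SAP 5.4.1 estimates recovery at 13, 18 and 24 months. Protocol 10.13.11 says that men who transition will be summarised with methods similar to those of the main analysis.

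**The concern.** In the sub-study the sponsor decided that a single non-castrate value is enough to end relugolix. The reason for that caution lasts as long as the two drugs are taken together: "Apalutamide is a strong inducer of CYP3A4 and a weak inducer of P-gp" (10.13.4.1), and the same section describes relugolix as cleared mainly by CYP3A and as a P-gp substrate. The supporting evidence there lowers the worry without removing it. The enzalutamide experience covers 17 men, and enzalutamide inhibits P-gp in vitro whereas apalutamide weakly induces it. For the 40 mg simulation only a median is reported.

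Two things are at stake. The first is treatment: the value that ends relugolix on Day 28 has no prescribed consequence at C4/D1, so sites could handle the same result differently in men with high-risk disease. The second is reporting: the recovery definition does not require that ADT has ended, so a man whose testosterone escapes to 150 ng/dL on relugolix could be tabulated as recovered.

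**Working it through.** **Inputs.** Cycle length is 28 days and there are 12 apalutamide cycles (Protocol 1.1). Main-study visits and their ±7 day window are in Protocol 1.3. The Day 28 visit has a +3 day window and relugolix starts on Day -14 (10.13.3). ADT lasts 12 months (1.1). There is no Day 0 (SAP 5.1).

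1. *The plan's own figure.* The exact one-sided 95% upper limit for 0 of 12 is 1 − 0.05^(1/12) = 0.2209, which matches the 22.1% in 10.13.11. One failure in 12 also passes the sub-study; its exact limit (95th percentile of Beta(2, 11)) is 33.9%. Both figures describe failure at Day 28, not later loss.

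2. *Visit days.* Cycle n Day 1 falls on Day 1 + (n − 1) × 28. This gives C3 = 57, C4 = 85, C7 = 169, C10 = 253 and C13 = 337.

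3. *First gap after the last covered value.* 85 − 28 = 57 days. Shortest with windows: (85 − 7) − (28 + 3) = 47. Longest: (85 + 7) − 28 = 64.

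4. *Later gaps.* 169 − 85 = 253 − 169 = 337 − 253 = 84 days each, or 70 to 98 with ±7 days at both ends.

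5. *Share of treatment after Day 28.* Apalutamide runs for 12 × 28 = 336 days, of which 336 − 28 = 308 (92%) come after Day 28. The first gap is 57/308 = 18.5% of those days.

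6. *Where a forced switch stops making sense.* Fourteen days of relugolix precede Day 1. Taking 12 months as 365 days, ADT ends near Day 365 − 14 = 351. C13/D1 (Day 337) is therefore about 14 days before the end, and a depot given then would prolong castration and delay recovery. C4/D1, C7/D1 and C10/D1 are the results for which a switch is useful.

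7. *Effect of a C3/D1 draw.* The first gap becomes 57 − 28 = 29 days, from (57 − 7) − (28 + 3) = 19 to (57 + 7) − 28 = 36 with windows, followed by 28 days to C4/D1.

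8. *Recovery.* One man who reaches 150 ng/dL on relugolix, and would not otherwise have recovered by the time point, adds 1/12 = 8.3 percentage points to this group's rate. If one man has already left relugolix at Day 28, he adds 1/11 = 9.1 points to the rate among the men who continue. Both ignore censoring. If he would have recovered by then anyway, only the timing shifts.

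**The case against.** The strongest reply is that the continuation is not unprotected.

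- Protocol 10.7 advises replacing drugs cleared mainly by CYP3A4 where possible, or otherwise checking that they still work; it gives similar cautionary advice for P-gp substrates. Section 10.13.8.6 applies this to the sub-study.
- Section 8.2.4 requires the investigator to review laboratory results and document the review.
- Day 28 was not arbitrary: 10.13.4.1 puts apalutamide steady state at 4 weeks, so that draw tests the interaction near its plateau.
- Visits 2 and 3 include drug accountability, and the calls in 10.10 ask about compliance with oral dosing.
- Men on depot ADT have no rule at 50 ng/dL either.

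Most of this stands, and it rules out reading the plan as giving investigators nothing to go on after Day 28. What it does not supply is a level, a time and an action. Section 10.7 calls for a check on efficacy, yet no testosterone is scheduled before Day 85. Adherence checks do not measure castration, and the missed-dose trigger loosens from 3 days or more (10.13.9.1) to more than 28 days (7.1). The depot comparison is weaker than it looks, because the interaction question in 10.13.4.1 concerns relugolix specifically. Whether the relugolix label asks for testosterone monitoring cannot be checked here.

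Two further inferences should not be drawn. A reader might think that the continuation dose is open, because 10.13.4.1 cites label advice "to increase the dose of relugolix to 240 mg once daily" with combined P-gp and strong CYP3A inducers. The hypothesis in that section and the dose justification in 10.13.6.3 both point to 120 mg, so this is no more than optional clarification. A reader might also think that the benefit-risk text in 10.13.4.2 misdescribes the continuation, but it is expressly about the 6-week sub-study.

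**Conclusion.** The gap is real but limited. The mandatory switch covers only Day 1 and Day 28, while relugolix with apalutamide may run for up to 11 more cycles. For C4/D1, C7/D1 and C10/D1 the protocol prescribes no action at 50 ng/dL or more. The group rule can still move a man to intramuscular ADT after his own Day 28, but only because of Day 28 values, never because of his own later result.

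At most 12 men are affected, or 11 if one fails at Day 28. It would be tempting to infer that late loss of castration is likely, or to carry the 22.1% limit forward as its rate. The documents give no rate after Day 28, so no probability is claimed. Nor is the primary result at risk: the sub-study men are additional to the 94 and are analysed separately (Protocol 1.1).

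The recovery point rests on one assumption, that the similar methods promised in 10.13.11 include the SAP 5.4 definition. The SAP does not mention the sub-study. On that assumption a rise to 150 ng/dL during ADT would count as recovery.

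The change should be made, because it mainly extends the sponsor's own rule at very little cost.

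**What to change.** 1. Extend footnote f to testosterone results at main-study visits through C10/D1 while a man is on relugolix. At 50 ng/dL or more, relugolix ends and he moves to intramuscular ADT, with total ADT still limited to 12 months. A prompt repeat and an adherence check before the switch are reasonable, since a single value may reflect missed tablets. At C13/D1 leave the decision to the investigator, because ADT is about to end.
2. For these men, add a testosterone draw at the existing C3/D1 visit (Day 57). The 84-day gaps after C4/D1 remain, but the results through C10/D1 then carry an action.
3. In the testosterone recovery analysis, count 150 ng/dL or more as recovery only after ADT has ended: after the last relugolix dose, or after the dosing interval of the last depot.

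Cost: at most 12 extra samples, a few sentences in Appendix 13 and one derivation rule in the SAP. No scheduled visits or participants are added; a repeat test would be needed only after a non-castrate result.
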